5.2. Exclusion Criteria

A subject will not be eligible for inclusion in this study if any of the following criteria apply:

CONCURRENT CONDITIONS/MEDICAL HISTORY (INCLUDES LIVER FUNCTION AND QTc INTERVAL)

1. **Concurrent Respiratory Disease:** Presence of a known pre-existing, clinically important lung condition other than asthma. This includes current infection, bronchiectasis, pulmonary fibrosis, bronchopulmonary aspergillosis, or diagnoses of emphysema or chronic bronchitis (chronic obstructive pulmonary disease other than asthma) or a history of lung cancer.
2. **Eosinophilic Diseases:** Subjects with other conditions that could lead to elevated eosinophils such as Hypereosinophilic Syndromes, including Churg-Strauss Syndrome, or Eosinophilic Esophagitis. Subjects with a known, pre-existing parasitic infestation within 6 months prior to Visit 1 are also to be excluded.
3. **Malignancy:** A current malignancy or previous history of cancer in remission for less than 12 months prior to screening (Subjects that had localized carcinoma of the skin which was resected for cure will not be excluded).
4. **Immunodeficiency:** A known immunodeficiency (e.g. human immunodeficiency virus – HIV), other than that explained by the use of corticosteroids taken as therapy for asthma.
5. **Other Concurrent Medical Conditions:** Subjects who have known, pre-existing, clinically significant cardiovascular, endocrine, autoimmune, metabolic, neurological, renal, gastrointestinal, hepatic, haematological or any other system abnormalities that are uncontrolled with standard treatment.
6. **Liver Disease:** Known, pre-existing, unstable liver disease (as defined by the presence of ascites, encephalopathy, coagulopathy, hypoalbuminaemia, esophageal or gastric varices or persistent jaundice), cirrhosis, and known biliary abnormalities (with the exception of Gilbert's syndrome or asymptomatic gallstones).
7. **ECG Assessment:** QT interval corrected for heart rate by either Fridericia's or Bazett's formula $QTc(F)/QTc(B) \geq 450\text{msec}$ or $QTc(F)/QTc(B) \geq 480\text{ msec}$ for subjects with Bundle Branch Block at Visit 1.

CONCOMITANT MEDICATIONS

8. **Xolair:** Subjects who have received omalizumab within 130 days of Visit 1.
9. **Other Monoclonal Antibodies not including mepolizumab:** Subjects who have received any monoclonal antibody (other than Xolair) to treat inflammatory disease within 5 half-lives of Visit 1.

- | |
|--|
| 
10. Investigational Medications: Subjects who have received treatment with an investigational drug, other than mepolizumab within the past 30 days or five terminal phase half-lives of the drug whichever is longer, prior to visit 1 (this also includes investigational formulations of marketed products) or experimental anti-inflammatory drugs (non biologicals) in the past 3 months.
 
11. Chemotherapy: Subjects who have received chemotherapy within 12 months prior to Visit 1.
 |
|--|

RELEVANT HABITS

- | |
|---|
| 
12. Alcohol/Substance Abuse: A history (or suspected history) of alcohol misuse or substance abuse within 2 years prior to Visit 1.
 |
|---|

CONTRAINDICATIONS

- | |
|---|
| 
13. Hypersensitivity: Subjects with hypersensitivity to mepolizumab or to any of the excipients (sodium phosphate, citric acid, sucrose, EDTA, polysorbate 80).
 |
|---|

DIAGNOSTIC ASSESSMENTS AND OTHER CRITERIA

- | |
|--|
| 
14. Adherence: Subjects who have known evidence of lack of adherence to controller medications and/or ability to follow physician's recommendations.
 |
|--|

5.3. Continuation to Treatment Criteria

At Visit 2, those subjects who continue to meet the inclusion/exclusion criteria and who meet the continuation to treatment criteria will commence the study treatment phase until the target of approximately 55 enrolled subjects is reached.

In order to receive study treatment subjects must have fulfilled all inclusion and exclusion criteria described in Section 5.1 and Section 5.2. In addition to the following:

REQUIRED CRITERIA TO START TREATMENT

- | |
|---|
| 
1. Liver Function: At Visit 2, ALL study subjects must fulfil the following additional criteria in order to be eligible for study treatment:
 
 • Liver Function Tests: obtained at Visit 1: 
 ○ Alanine aminotransferase (ALT) $\leq 2x$ ULN (upper limit of normal) ○ Bilirubin $\leq 1.5x$ ULN (isolated bilirubin $> 1.5x$ ULN is acceptable if bilirubin is fractionated and direct bilirubin $< 35\%$) 
2. Eosinophilic Phenotype: At Visit 2, study subjects that were NOT receiving mepolizumab treatment at Visit 1 must fulfil the following additional criteria in order to be eligible for study treatment:
 |
|---|

- Airway inflammation characterised as eosinophilic in nature as indicated by one of the following:
 - a) A peripheral blood eosinophil count of ≥ 300 cells/ μL that is related to asthma demonstrated in the past 12 months prior to Visit 1.
- OR**
- b) A peripheral blood eosinophil count of ≥ 150 cells/ μL at Visit 1 that is related to asthma.

5.4. Pre-Screening/Screening Failures

A subject will be assigned a subject number at the time the informed consent is signed.

A subject who is assigned a subject number at Visit 0 but does not have any screening Visit 1 procedures will be considered a pre-screen failure.

Screen failures will be defined as those subjects who complete at least one Visit 1 (Screening) procedure but do not attempt to self-administer a dose of mepolizumab.

The following information will be collected in the electronic case report form (eCRF) for subjects who are pre-screen and screen failures:

- Date of Informed Consent Form (ICF) signature
- Demographic information including race, age and gender
- Child bearing status assessment for all female subjects of reproductive potential
- Subject number
- Details of asthma medications within 3 months of the pre-screening Visit 0
- Details of asthma exacerbations during the pre-screening period
- Serious Adverse Event information only for any SAE considered as related to study participation (e.g. protocol mandated procedures, invasive tests or change in existing therapy) or related to a GSK concomitant medication
- Investigator signature page

In order to ensure transparent reporting of screen failure subjects, meet the Consolidated Standards of Reporting Trials (CONSORT) publishing requirements, and respond to queries from Regulatory authorities, a minimal set of screen failure information is required including Demography, Screen Failure details, Eligibility Criteria, and Serious Adverse Events (see Section [7.7.1](#)).

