6.7. Training Session

Training of study treatment, handling and administration techniques by qualified study site personnel will be provided to the study participants at Visit 2 prior to self-administration. The training is designed to be representative of the instruction and training materials that will be used in the post-marketing setting. The training will consist of a walk-through of the IFU for the injection devices by the site personnel. Finally, the first actual injection will then be supervised by site personnel including feedback to the subject as needed.

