9.3.1. Analysis Populations

All Subjects Population

The 'All Subjects' population will comprise all enrolled subjects (i.e. attempting at least one self-administration of mepolizumab). This population will be used for the evaluation of the mepolizumab liquid drug product in safety syringe and for the summaries relating to the safety and tolerability of mepolizumab.

PK Population:

The PK population will be defined as all enrolled subjects for whom at least one PK sample was obtained and analyzed. This will be the primary population for assessing PK.

PD Population:

The PD population is defined as all enrolled subjects who also have a baseline PD measurement and at least one post-treatment PD measurement. This will be the primary population for assessing PD.

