4. ANALYSIS POPULATIONS

Population	Definition / Criteria	Analyses Evaluated
All Subjects Enrolled (ASE)	
 All subjects for whom a record exists in the data base. 	
 Pre-screen and screen failures
All Subjects (Safety)	
 All enrolled subjects attempting at least one self-administration of mepolizumab. 	
 Endpoints relating to safety syringe use and functionality, including primary endpoint Study Population Safety
Pharmacokinetic (PK)	
 All enrolled subjects attempting at least one self-administration of mepolizumab for whom a PK sample was obtained and analysed. 	
 PK
Pharmacodynamic (PD)	
 All enrolled subjects attempting at least one self-administration of mepolizumab who had a baseline PD measurement and at least one post-treatment PD measurement. 	
 PD

NOTES :

- Please refer to Appendix 8: List of Data Displays which details the population to be used for each displays being generated.

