7.2. Other Analyses to Evaluate Safety Syringe

The following endpoints will be summarised in the same way as the primary endpoint (Section 7.1).

- The number and percentage of subjects successfully able to self-administer their unobserved second dose at Week 4. The denominator for the percentage calculation will be the number of subjects attempting an injection at Week 4.
- The number and percentage of subjects successfully able to self-administer their observed first dose at Week 0. The denominator for the percentage calculation will be the number of subjects attempting an injection at Week 0.
- The number and percentage of subjects successfully able to self-administer both their unobserved second dose at Week 4 and their observed third dose at Week 8. The denominator for the percentage calculation will be the number of subjects attempting an injection at both Week 4 and Week 8.

- The number and percentage of subjects successfully able to self-administer all three doses at Week 0, 4 and 8. The denominator for the percentage calculation will be the number of subjects attempting all three doses at Week 0, 4 and 8.

Table 3 provides an overview of the analyses to evaluate the safety syringe, with full details of data displays being presented in Appendix 8: List of Data Displays.

Table 3 Overview of Analyses to Evaluate Safety Syringe

	Summary		Individual	
	T	F	F	L
Primary Endpoint				
Proportion of subjects successfully able to self-administer their observed third dose at Week 8.	Y			Y
Secondary Endpoint				
Proportion of subjects successfully able to self-administer their unobserved second dose at Week 4.	Y			Y
Other Endpoint				
Proportion of subjects successfully able to self-administer their observed first dose at Week 0.	Y			Y
Proportion of subjects successfully able to self-administer their unobserved second dose at Week 4 and their observed third dose at Week 8.	Y			Y
Proportion of subjects successfully able to self-administer all three doses at Week 0, 4 and 8.	Y			Y
Investigator assessment of user/device errors by visit	Y			Y
Observer checklist for in-clinic injections	Y			Y ¹
Subject completed checklist for home injection	Y			Y ¹
Device usability/functionality subject completed questionnaire	Y			

NOTES :

- T = Table, F = Figure, L = Listing, Y = Yes display generated.
- Summary = Represents TFL related to any summaries (i.e. descriptive statistics) of the observed raw data.

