14.5. Appendix 5: Premature Withdrawals & Handling of Missing Data

14.5.1. Premature Withdrawals

Element	Reporting Detail
General	
 • Subject study completion is defined as completion of the End of Study (Week 12) visit. • Withdrawn subjects will not be replaced in the study. • All available data from subjects who were withdrawn from the study will be listed and all available planned data will be included in summary tables and figures, unless otherwise specified.
Pre-Screen and Screen Failures	
 • A subject will be assigned a subject number at the time when the informed consent form (ICF) is signed. • A subject who is assigned a subject number but does not have any screening procedures at Visit 1 will be considered a pre-screen failure. • A subject who completes at least one Visit 1 procedure but does not attempt to self-administer a dose of mepolizumab will be considered a screen failure.

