userid: /arenv/arprod/compound/study/final/drivers/drivername.sas DDMMYYYY HH:MM

Example TAB_INJ1
Protocol: MID205667
Population: All Subjects (Safety)

Table X
Summary of Proportion of Subjects Successfully Able to Self-Administer Injection by Visit

Visit	Liquid Safety Syringe (N = XX)		
	Attempted Injections	Successful Injections [1]	
	n (%)	n (%)	95% CI
WEEK 0	XX (XX%)	XX (XX%)	(XX%, XX%)
WEEK 4	XX (XX%)	XX (XX%)	(XX%, XX%)
WEEK 8	XX (XX%)	XX (XX%)	(XX%, XX%)
WEEK 4 and 8	XX (XX%)	XX (XX%)	(XX%, XX%)
WEEK 0, 4 and 8	XX (XX%)	XX (XX%)	(XX%, XX%)

[1] The denominator for the percentage of successful injections is the number of attempted injections.

CONFIDENTIAL

205667

Example TAB_INJ2
 Protocol: MID205667
 Population: All Subjects (Safety)

Page 1 of 1

Table X.X
 Summary of Investigator Evaluation of User/Device Errors by Visit

Visit	n		Liquid Safety Syringe (N=XX)
WEEK 0	XX	Was the drug successfully injected?	
		Yes	XX (XX%)
		No	XX (XX%)
		Not attempted	XX (XX%)
		User Error	
		Any User Error	XX (XX%)
		Ring cap not removed from autoinjector	XX (XX%)
		Autoinjector not properly activated on injection site (e.g., gold needle guard not flush with skin)	XX (XX%)
		Autoinjector used upside down	XX (XX%)
		Autoinjector pulled away before end of injection (i.e., before purple indicator stopped moving)	XX (XX%)
		Other	XX (XX%)
		Device Error	
		Any Device Error	XX (XX%)
		Autoinjector leaking	XX (XX%)
		Components missing / broken / cracked	XX (XX%)
		Inspection window not clear	XX (XX%)
		Cannot remove ring cap	XX (XX%)
		Bent needle	XX (XX%)
		Cannot push the gold needle guard down to activate (i.e., force too high)	XX (XX%)
		Autoinjector does not activate (after pressing gold needle guard down)	XX (XX%)

Programming Note: Continue for Week 4 and 8

userid: /arenv/arprod/compound/study/final/drivers/drivername.sas DDMMYYYY HH:MM

Example TAB_INJ3
 Protocol: MID205667
 Population: All Subjects (Safety)

Table X.X
 Summary of Observer Checklist for In-Clinic Injections

Visit: WEEK 0

Liquid Safety Syringe
 (N=XX)

Time from removal of syringe from storage to injection (mins)	n	XX
	Mean	XX.X
	SD	XX.XX
	Median	XX.X
	Minimum	XX
	Maximum	XX
Confirm who will be administering the injection	n	XX
	Patient	XX (XX%)
	Caregiver	XX (XX%)
Subject/caregiver completed all the training required	n	XX
	Yes	XX (XX%)
	No	XX (XX%)
Subject/caregiver had instructions for use (IFU) available for review during injection (as recommended)	n	XX
	Yes	XX (XX%)
	No	XX (XX%)

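### A subject trained at Visit 2 who cannot bring themselves to inject becomes a screen failure, so neither the success proportions nor the SAP 7.1 sensitivity analysis can count them

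*Protocol*

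**What the plan says.** Protocol 5.4 defines screen failures as subjects "who complete at least one Visit 1 (Screening) procedure but do not attempt to self-administer a dose of mepolizumab". SAP 14.5.1 has the same rule: a subject with a Visit 1 procedure who "does not attempt to self-administer a dose of mepolizumab will be considered a screen failure". Under Protocol 6.7, training "will be provided to the study participants at Visit 2 prior to self-administration", that is, at the visit where eligibility and the continuation criteria of Protocol 5.3 have already been settled.

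The analysis population for the device endpoints, All Subjects (Safety), is defined in SAP section 4 as "All enrolled subjects attempting at least one self-administration of mepolizumab"; Protocol 9.3.1 agrees. The denominators of all five success proportions (Week 0, Week 4, Week 8, Weeks 4 and 8, all three doses) are subjects who attempted the injections concerned. For the first dose, SAP 7.2 states: "The denominator for the percentage calculation will be the number of subjects attempting an injection at Week 0".

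SAP 7.1 plans one sensitivity analysis, of the primary endpoint. After withdrawal from study treatment because of problems with the syringe, missing results, and results recorded as not attempted, are counted as failures. SAP section 7 bases all these analyses on All Subjects (Safety).

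**The concern.** Protocol section 3 gives the aim as the proportion of subjects with severe eosinophilic asthma who can give a dose themselves or through a caregiver, under conditions meant to resemble real use. A subject who starts and fails a critical step counts against the syringe (Protocol 7.3). A subject who is trained and cannot start is removed from the population. That is selection on something very close to the outcome.

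Two features add to this. Treatment starts continue until about 55 subjects are enrolled (Protocol 5.3), and enrolled means having attempted (Protocol 4.3), so a trained non-attempter is in effect replaced, whereas SAP 14.5.1 does not replace withdrawn subjects. And neither document defines an attempt, so in an open-label study a subject who uncaps the syringe and stops could be classed either as a failed injection or as a screen failure.

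At stake is whether the report can show that no trained subject was lost at the point of injecting, or how many were.

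**Working it through.** **Following one subject through the text.**
1. The subject has Visit 1 procedures, meets the continuation criteria and is trained at Visit 2 (Protocol 5.3, 6.7).
2. The subject does not inject, and no caregiver injects.
3. With a Visit 1 procedure and no attempt, the subject is a screen failure (Protocol 5.4, SAP 14.5.1).
4. With no attempt, the subject is not in All Subjects (Safety) (Protocol 9.3.1, SAP section 4), so is in none of the five denominators (Protocol 9.4.1, SAP 7.1 and 7.2).
5. The SAP 7.1 sensitivity analysis runs inside that population, so it cannot bring the subject back.
6. The subject remains only in All Subjects Enrolled displays, such as the screen-failure summary and listing.

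**The plan's own figures.** The exact (Clopper-Pearson) method with n = 50 reproduces all 11 rows of the precision table in Protocol 9.2.2. For example, 45/50 gives 78.19 to 96.67 (stated 78, 97) and 49/50 gives 89.35 to 99.95 (stated 89, 100). The same method is used below.

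**Size.** Inputs: n = 55 attempters at Week 0 and n = 50 at Week 8, from the planned enrolled and completed numbers (Protocol 9.2.1). The number of successes x and the number k of use-related trained non-attempters are not in the documents; both are assumptions.

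Counting the k subjects as unsuccessful changes x/n to x/(n+k), a fall of (x/n) × k/(n+k). This cannot be negative, and it is zero when k = 0.

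| k | Week 0, x = 55 of 55 | Week 0, x = 52 of 55 | Week 8, x = 49 of 50 |
|---|---|---|---|
| 0 | 100% (93.5–100) | 94.5% (84.9–98.9) | 98.0% (89.4–99.9) |
| 1 | 98.2% (90.4–100.0) | 92.9% (82.7–98.0) | 96.1% (86.5–99.5) |
| 2 | 96.5% (87.9–99.6) | 91.2% (80.7–97.1) | 94.2% (84.1–98.8) |
| 3 | 94.8% (85.6–98.9) | 89.7% (78.8–96.1) | 92.5% (81.8–97.9) |
| 5 | 91.7% (81.6–97.2) | 86.7% (75.4–94.1) | 89.1% (77.8–95.9) |

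Range of the fall:
- Week 0, x from 50 to 55. For k = 1: 50/55 × 1/56 = 1.6 points to 55/55 × 1/56 = 1.8 points. For k = 5: 50/55 × 5/60 = 7.6 points to 55/55 × 5/60 = 8.3 points.
- Week 8, x from 45 to 50. For k = 1: 45/50 × 1/51 = 1.8 points to 50/50 × 1/51 = 2.0 points. For k = 5: 45/50 × 5/55 = 8.2 points to 50/50 × 5/55 = 9.1 points.

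**The case against.** The strongest reply is that the plan states its target openly. The proportions are among attempters, success is defined by handling steps and syringe inspection, and a proportion among all trained subjects is a different quantity. That stands as a reason to leave the primary analysis alone. It does not settle the matter, because SAP 7.1 itself accepts that a syringe-related non-attempt is a failure and then stops short of the visit where a first refusal would occur.

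The affected group may be small. Caregiver injection counts as self-administration, subjects have consented to a self-injection study, and someone who begins but cannot finish is already scored as a failure. There is also no hypothesis or success threshold for a shift of two points to cross. All of this limits the size; none of it closes the gap.

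Four stronger readings are tempting, and the documents do not support them:
- A reader might infer that the screen-failure label biases the primary estimate. The Week 8 denominator leaves out non-attempters at that visit whatever they are called, so relabelling alone would not move it.
- A reader might infer that the Week 0 row "Not attempted" in shell TAB_INJ2 can never be filled. The population needs one attempt at any dose, not at Week 0. The shell also continues to Weeks 4 and 8, where the row is needed.
- A reader might infer that the screen-failure displays hide these subjects among the 75 − 55 = 20 planned losses before enrolment. The ES6 and ES7 templates are not shown and the listing gives reasons, so this cannot be established. What can be said is that no display is specified to count them.
- A reader might infer that every trained non-attempter should count as a failure. A positive pre-dose pregnancy test, intercurrent illness or an unrelated withdrawal of consent would then become a device failure, which is bias in the other direction.

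**Conclusion.** The gap is real and limited. An eligible, trained subject who does not inject for use-related reasons, and has no caregiver who does, is outside the analysis population and beyond the sensitivity analysis. If any such subjects exist, the success proportions overstate the ability to self-administer relative to the stated aim. The direction is certain whenever k is above zero; the size is not known. Assuming 50 to 55 attempters and success of at least 90%, the first such subject costs 1.6 to 2.0 points and five would cost 7.6 to 9.1 points. The documents do not suggest that five is likely, and with none the effect is zero. This calls for a supplementary analysis and a reported count, not a new primary analysis.

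**What to change.** Keep the primary analysis and the Safety population as they are, and make three changes.

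1. Record every subject trained at Visit 2 who does not attempt an injection, with the reason, and state in one line what counts as an attempt. Report the number alongside TAB_INJ1.
2. Extend the SAP 7.1 sensitivity analysis to the set of eligible subjects who began training at Visit 2. Apply it to Week 8 and also to the Week 0 and all-three-doses endpoints.
3. In that analysis, count as unsuccessful only those who did not attempt because of problems with using the syringe or with self-injection. Subjects stopped for unrelated reasons are shown in the count but not scored as failures, in keeping with the restriction SAP 7.1 already makes.

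The cost is one eCRF flag with a reason field, a short wording change to both the protocol and the SAP, and possibly slightly less favourable sensitivity figures. In return, if there are no such subjects, the report can say so.

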5.5. Withdrawal/Stopping Criteria

A subject may withdraw from study treatment at any time at his/her own request, or may be withdrawn at any time at the discretion of the investigator for safety, behavioural, or

administrative reasons. If a subject withdraws from the study, he/she may request destruction of any samples taken, and the investigator must document this in the site study records. As the aim of this study is to evaluate the use of the mepolizumab liquid drug product, in safety syringe presentation, for delivery of mepolizumab, subjects who permanently withdraw from study treatment will also be withdrawn from the study (see Section 5.5.1). Reasons for premature discontinuation of study treatment will be captured in the CRF.

